2.4 Discontinuation Criteria

First, during the course of medication, if the subject develops an aggravation of the condition

he/she should discontinue the use of the test drug, complete the post-evaluation of the efficacy and the relevant laboratory tests to end the trial, and the subject will be counted as an invalid eligible case for inclusion in the PPS. Second, if the investigator believes that other circumstances make it inappropriate for the subject to continue using the test drug.

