2.6.4 Efficacy indicators

Main efficacy indicator is DFS. Refers to the time between the start of randomisation and disease recurrence or death (from any cause). Imaging: Chest CT examination before the start of treatment and every 6 months after surgery. Patients found to have recurrent metastases were discharged from the group for standardised treatment when the pathological diagnosis was clear. Observation and follow-up until 5 years after surgery, disease-free survival rate, disease-free survival and median survival calculation. Secondary efficacy indexes includes OS, MRD, Circulating tumour cells detection, TCM symptom score, QoL, Immune indicators, Tumour markers, SII, PIN, PNI.

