OS: Endpoint indicator, defined as the time from the start of randomisation to death due to any cause. Overall survival and median survival calculations were performed with observational follow-up up to 5 years postoperatively. MRD: Second-generation sequencing NGS method is used to detect MRD in peripheral blood of the study subjects to obtain the superior population screening model for TCM treatment; Circulating tumour cell detection: Detect 1 time each before and after intervention. Specimen collection method: 10ml of venous blood was taken from the patient's median elbow vein with EDTA blood collection tube, the blood collection tube was repeatedly inverted and mixed, centrifuged at 2000g for 10min, the supernatant was retained, and in order to further remove the redundant cellular components, it should be centrifuged again at 8000g for 10min. Separated plasma was frozen and stored at -80°C or extracted immediately according to the extraction kit instruction steps respectively. The remaining blood cells should be added to saline to replenish 10ml and then immediately isolate the circulating tumour cells. TCM symptom score: According to the "Shanghai TCM disease diagnosis and treatment routine", 10 TCM symptoms of cough, sputum, chest pain, chest tightness, shortness of breath, fatigue, loss of appetite, insomnia, dry mouth and throat and spontaneous sweating were observed, and the severity was scored according to 0-3, which was recorded once before and 6 months after the intervention. Significant effect: the reduction of TCM symptom score is greater than or equal to 70% after the intervention; Effective: the reduction of TCM symptom score is greater than or equal to 30% and less than 70% after the intervention; Ineffective: the reduction of TCM symptom score is less than 30% after the intervention or elevated compared with the previous one. Quality of life assessment: The Quality of Survival Scale for Lung Cancer Patients EORTC QLQ-LC43 was used, which consists of EORTC QLQ-C30 (core scale) and EORTC QLQ-LC13 Th (characteristic subscale of lung cancer). It mainly scores lung cancer patients on 5 domains related to functioning, general clinical symptoms, characteristic sub-symptoms, general health status and

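### Protocol 2.4 ends the patient's trial, not only the study drug, at an undefined worsening; read literally, this cuts short OS follow-up, and DFS follow-up too where recurrence is unconfirmed

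*Protocol*

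**What the plan says.** Protocol 2.4 has two criteria. The first applies during dosing, which 2.3 sets at 6 months. Its trigger is an aggravation of the patient's condition, with no definition and no confirmation rule. The consequence is that "he/she should discontinue the use of the test drug, complete the post-evaluation of the efficacy and the relevant laboratory tests to end the trial", and then "the subject will be counted as an invalid eligible case for inclusion in the PPS". The second criterion leaves it to the investigator whether other circumstances make further use of the drug inappropriate. It speaks of the drug only.

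Elsewhere the Protocol plans long follow-up:

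- **DFS (primary, 2.6.4).** Time from randomisation to recurrence or death from any cause, with "Chest CT examination before the start of treatment and every 6 months after surgery" and "Observation and follow-up until 5 years after surgery".
- **OS (secondary, 2.6.4).** Time from randomisation to death from any cause: "Overall survival and median survival calculations were performed with observational follow-up up to 5 years postoperatively".
- **Analysis (Statistical Analysis).** Kaplan-Meier curves and a stratified Cox model for DFS and OS, on an ITT basis.

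Three other places bear on who stays in follow-up. Section 2.3 lets follow-up stop at 5 years, at death or, in brackets, at progression. Section 2.6.4 says: "Patients found to have recurrent metastases were discharged from the group for standardised treatment when the pathological diagnosis was clear". Section 2.5.1 makes a general commitment to track the research subjects over the long term.

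**The concern.** Stopping a drug and leaving a trial are different events. A patient who stops the granules can still be scanned, and survival status can still be recorded. If a site follows 2.4 as written, that stops. No sentence in the Protocol says that a patient who exits under this criterion stays in follow-up.

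What is lost depends on what the trigger means:

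1. **Confirmed recurrence.** The DFS event has been observed, so DFS is intact. OS after that date is not collected.
2. **Also symptomatic or unconfirmed worsening.** DFS follow-up stops without an event, and OS is lost as well.

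Patients censored in this way leave because they are deteriorating. Kaplan-Meier and Cox estimates assume that censoring is unrelated to prognosis, given what the model contains. An analysis plan cannot recover data that were never collected.

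**Working it through.** **Step 1: is the second reading realistic?** Section 1.2 enrols patients no later than 6 weeks after surgery, and CT is every 6 months (26 weeks) after surgery. The first scheduled CT after baseline therefore falls 26 − 6 = 20 to 26 − 0 = 26 weeks after randomisation. If dosing starts at randomisation (assumed), that is near the end of the 6 months. Earlier worsening would appear as symptoms or on unscheduled tests. So unconfirmed worsening during dosing is possible. This does not show that patients would leave without a work-up.

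**Step 2: the plan's own figure.** Inputs from 1.4: 5-year DFS 0.783 (control) and 0.90 (treatment), one-sided α 0.025, power 0.80, 10% dropout.

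- HR = ln 0.90 / ln 0.783 = 0.431.
- Schoenfeld events = 4 × (1.960 + 0.842)² / (ln 0.431)² ≈ 44.3, rounded up to 45.
- Mean 5-year event probability = (0.217 + 0.10)/2 = 0.1585.
- N = 45 / 0.1585 = 284, and 284 / 0.9 = 316, against 317 stated. The figure reproduces.

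**Step 3: baseline for the final sample size.** With 178 per arm and 5 years of follow-up for all, events = 178 × 0.217 + 178 × 0.10 = 38.6 + 17.8 = 56.4. Power = Φ(√56.4 / 2 × |ln 0.431| − 1.960) = 88.6%.

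**Step 4: illustration of early exit without a DFS event.** The Protocol gives no exit rate. Assume that a share q of each arm leaves at 3 months and is censored, that there is no other dropout, and that hazards are constant: −ln 0.783 / 5 = 0.0489 per year and −ln 0.90 / 5 = 0.0211 per year. Events per arm = 178 × [(1 − q)(1 − e^(−5λ)) + q(1 − e^(−0.25λ))].

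| q (assumed) | Control | Treatment | Total | Power |
|---|---|---|---|---|
| 0% | 38.6 | 17.8 | 56.4 | 88.6% |
| 5% | 36.8 | 17.0 | 53.8 | 87.0% |
| 10% | 35.0 | 16.1 | 51.1 | 85.3% |
| 20% | 31.3 | 14.4 | 45.8 | 81.3% |
| 30% | 27.7 | 12.7 | 40.4 | 76.4% |

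The table shows loss of information only. It gives leavers the average hazard and equal exit in both arms, so it contains no bias. If leavers have a worse prognosis, a given q would cost more events than shown.

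**Step 5: how much of the OS problem sits in 2.4 itself?** Expected DFS events within the 6 months of dosing are 178 × (1 − e^(−0.0489 × 0.5)) + 178 × (1 − e^(−0.0211 × 0.5)) = 4.30 + 1.87 = 6.2, and 6.2 / 56.4 = 11%. Under the confirmed-recurrence reading, 2.4 touches only that early share. The bracketed stop in 2.3 and the discharge sentence in 2.6.4 reach recurrences at any time.

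**The case against.** The strongest reply is that the Protocol intends to follow everyone. Section 2.5.1 promises long-term tracking without exempting patients who stop the drug, and neither the OS definition nor the ITT statement makes an exception. The English is loose, so ending the trial may mean no more than an end-of-treatment assessment. Where a dropout is meant, the Protocol says so: 2.1 treats a patient whose emergency letter is opened as a dropout, while 2.4 keeps its patients as eligible cases. Section 1.5 names disease progression in a parallel rule, which favours the confirmed-recurrence reading, and 2.4 orders an efficacy evaluation before exit.

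Most of this stands as evidence of intent. It does not remove the problem. Section 2.4 is the specific instruction a site would follow, the general sentence in 2.5.1 does not name these patients, and the nearest related sentences (2.3 and the discharge sentence in 2.6.4) also point towards ending follow-up. If full follow-up is intended, saying so costs little.

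Three stronger readings are tempting, and the documents do not support them:

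- **That DFS follow-up is certainly lost.** It is lost only if unconfirmed worsening counts as the trigger.
- **That the label in 2.4 turns worsening into a DFS failure.** Invalid most likely means ineffective, a category that 2.6.4 defines for the symptom score: "Ineffective: the reduction of TCM symptom score is less than 30% after the intervention". No text assigns it to DFS.
- **That the roughly 6 DFS events in the dosing window cap the loss, so that the effect on power must be small.** They do not. A patient who exits without recurrence also loses any later event over the remaining years, and the number of such patients is unknown.

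**Conclusion.** The point holds as a defect of wording that should be fixed, with medium confidence. Read literally, the first criterion of 2.4 cuts short OS follow-up under either meaning of the trigger, and DFS follow-up where the worsening is not a confirmed recurrence. The same OS loss after recurrence follows from 2.3 and 2.6.4 for the whole of follow-up.

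Neither the size nor the direction of the bias can be computed, because the Protocol gives no exit rate and no split by arm. The illustration (power from about 89% down to between 87% and 76% for assumed exits of 5% to 30%) rests on constant hazards, exit at 3 months, equal exit in both arms and no other dropout. It is not an estimate of what will happen. For OS nothing can be quantified, since the Protocol gives no OS assumption for the two arms.

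**What to change.** - **2.4:** replace the words that end the trial with stopping the study drug only. Keep the scheduled 6-monthly CT and DFS follow-up until confirmed recurrence, death, 5 years or withdrawal of consent.
- **2.3:** limit the bracketed stop at progression to DFS follow-up.
- **2.6.4:** state that patients discharged for recurrence stay in survival-status follow-up for OS to 5 years. Without this, editing 2.4 and 2.3 leaves the OS gap open.
- **DFS event:** state that only recurrence or death counts, whatever label 2.4 gives the patient.

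When to stop the granules remains a clinical decision. The cost is a few sentences, and the CTs are already scheduled. The real burden is that sites must keep contact with patients who stop the drug or relapse, and record their survival status.

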2.5 Data Collection and Management

2.5.1 Data management system

All the original data in the case report form will be backed up and entered into the database by two people, proofread each other and correct the entry errors, and after checking the accuracy with the original data in the case report form, the data will be locked and then statistically analysed. Construct a high-quality clinical research database, incorporate it into the unified management of the big data platform of the Oncology Research Centre, and conduct long-term tracking and follow-up of the research subjects.

2.5.2 Establishment of Data Steering Committee

The subject leader, statisticians and clinical scholars will work together to formulate standard treatment protocols, design trial protocols, organise the formulation and approval of various standard operating procedures, organise the formulation and approval of research plans, approve and decide whether to continue the trial, as well as approve the dissemination of trial results and write reports on the results.

2.5.3 Establishment of a Data Safety and Monitoring Board (DSMB)

Investigators (clinicians, not involved in the inclusion of participants) and statisticians were responsible for designing the CRF, assessing the adequacy of the participant recruitment process, evaluating data quality, outcome safety assessment, outcome and effect assessment, recommending continuation of the trial, and reviewing and approving the dissemination of the results and the draft report: a database administrator (full-time) was responsible for the management of the database; an ombudsman was responsible for the monitoring of the data: a data entry clerk 2 persons responsible for data entry.

2.5.4 Data capture and database management

Accurately collect and record process management information data and resultant measurement indicators and inspection data of observation items. A two-person, two-track entry into the electronic case information system (EDC) system is used, and after the entry is completed, the double data are checked and logical consistency verified. The database uses EDC for data management.

2.5.5 Data security and monitoring

Data monitoring before the start of the clinical trial is generally on-site verification; real-time online monitoring and online quality control of the EDC system during the trial; the final data monitoring is carried out after the completion of the trial data collection, and the external data materials are reviewed and accepted.

2.5.6 Database Locking

After the completion of the interim analysis of the clinical trial and the data monitoring at the end of the trial, report to the DSMB, the subject leader, with a list of data monitoring, and lock the database after obtaining a written signature of approval.

2.6 Outcomes

2.6.1 Baseline data observation

Demographic data: gender, age, height, weight, etc.; Vital signs: such as blood pressure, heart rate,

respiration, etc.; General clinical data: co-morbidities and medications, etc.; Other data: such as education level, marital status, etc.

2.6.2 Baseline tumour assessment and risk factors

Time of diagnosis, pathological type, degree of differentiation, tumor node metastasis (TNM) classification of tumour, gene mutation status, etc.; Comorbidities; Surgical procedure, history of preoperative adjuvant therapy; Smoking status; family history of illness.

2.6.3 Safety indicators

Blood routine; Liver and kidney functions: alanine aminotransferase (ALT), methionine aminotransferase (AST), glutamyl transpeptidase (γ -GT), blood creatinine (CREA), urea nitrogen (BUN), urinary protein (UPr), etc.; Electrocardiogram; Adverse events and serious adverse events (detailed records at any time). The above examinations were tested once before the test, once every month during the treatment period, and once every 6 months during the follow-up period.

2.6.4 Efficacy indicators

Main efficacy indicator is DFS. Refers to the time between the start of randomisation and disease recurrence or death (from any cause). Imaging: Chest CT examination before the start of treatment and every 6 months after surgery. Patients found to have recurrent metastases were discharged from the group for standardised treatment when the pathological diagnosis was clear. Observation and follow-up until 5 years after surgery, disease-free survival rate, disease-free survival and median survival calculation. Secondary efficacy indexes includes OS, MRD, Circulating tumour cells detection, TCM symptom score, QoL, Immune indicators, Tumour markers, SII, PIN, PNI.

OS: Endpoint indicator, defined as the time from the start of randomisation to death due to any cause. Overall survival and median survival calculations were performed with observational follow-up up to 5 years postoperatively. MRD: Second-generation sequencing NGS method is used to detect MRD in peripheral blood of the study subjects to obtain the superior population screening model for TCM treatment; Circulating tumour cell detection: Detect 1 time each before and after intervention. Specimen collection method: 10ml of venous blood was taken from the patient's median elbow vein with EDTA blood collection tube, the blood collection tube was repeatedly inverted and mixed, centrifuged at 2000g for 10min, the supernatant was retained, and in order to further remove the redundant cellular components, it should be centrifuged again at 8000g for 10min. Separated plasma was frozen and stored at -80°C or extracted immediately according to the extraction kit instruction steps respectively. The remaining blood cells should be added to saline to replenish 10ml and then immediately isolate the circulating tumour cells. TCM symptom score: According to the "Shanghai TCM disease diagnosis and treatment routine", 10 TCM symptoms of cough, sputum, chest pain, chest tightness, shortness of breath, fatigue, loss of appetite, insomnia, dry mouth and throat and spontaneous sweating were observed, and the severity was scored according to 0-3, which was recorded once before and 6 months after the intervention. Significant effect: the reduction of TCM symptom score is greater than or equal to 70% after the intervention; Effective: the reduction of TCM symptom score is greater than or equal to 30% and less than 70% after the intervention; Ineffective: the reduction of TCM symptom score is less than 30% after the intervention or elevated compared with the previous one. Quality of life assessment: The Quality of Survival Scale for Lung Cancer Patients EORTC QLQ-LC43 was used, which consists of EORTC QLQ-C30 (core scale) and EORTC QLQ-LC13 Th (characteristic subscale of lung cancer). It mainly scores lung cancer patients on 5 domains related to functioning, general clinical symptoms, characteristic sub-symptoms, general health status and

financial difficulties, and is recorded once before and 6 months after the intervention. The higher the score of function-related domains, the worse the function of the organism; the higher the score of general clinical symptoms and characteristic sub-symptoms, the more serious the symptoms; the higher the score of general health status, the better the status; the higher the score of economic hardship status, the more difficult the economic hardship. Immune indicators: Cellular immunity (CD3, CD4, CD8, CD16, CD56), regulatory T cells, myeloid-derived suppressor cells MDSCs, natural killer cells NK, IL-1, IL-2, IL-6, IL-8, IL-10. 1 test before and 6 months after intervention. Tumour markers: CEA, CA125, CA153, Cyfra21-1, SCC before and after treatment. At least 1 test before intervention and 6 months after intervention. SII and PIN: The inflammatory response, immune status and nutritional status of the body affect the tumour microenvironment and prognosis of tumour patients. Studies have shown that tumour-associated inflammation, especially host-associated systemic inflammation, is closely related to tumour development and progression, as well as survival of cancer patients. SII is a comprehensive immune-inflammatory index, calculated based on the results of platelet, neutrophil, and lymphocyte counts. SII is a more objective predictor of the prognosis of patients with various types of tumours. It represents the balance between inflammation and immunity in tumour patients. Inflammation, in turn, can influence tumour progression by affecting the host's immunity and response to anti-tumour therapy. PNI is a nutritional prognostic indicator that can be used to reflect the nutritional and immune status of tumour patients and is calculated from serum albumin and circulating lymphocyte counts. PNI is a nutritional prognostic indicator that can be used to reflect the nutritional and immune status of tumour patients. Malnutrition is very common in patients with malignant tumours, especially advanced tumours. Day plays a crucial role in the process of tumour progression. There is also a relationship between tumour-associated inflammation and nutritional status. Studies have shown that tumour-secreted inflammatory mediators, including tumour necrosis factor (TNF) and IL-6, lead to a loss of appetite and affect nutritional intake. And nutritional and immune status is associated with tumour progression and prognosis. The formula is as follows: SII=peripheral blood platelet count ($\times 10^9/L$) \times peripheral blood neutrophil count ($\times 10^9/L$)/peripheral blood lymphocyte count ($\times 10^9/L$). PNI: Serum albumin(g/L)+Lymphocyte count($10^9/L$) $\times 5$. Critical values were calculated based on ROC curves, and based on the critical values, the above indexes were divided into high level and low level groups.

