1.4 Sample Size

The calculation of the sample size of this clinical trial is based on the statistical results of the "Chinese Medicine Clinical Research on Common Malignant Tumours (Lung Cancer)" conducted by this group in the Third Round of Shanghai Three-Year Action Plan of Traditional Chinese Medicine. Based on the group's previous clinical research on the survival and immune function effects on patients after radical NSCLC surgery, the 5-year disease-free survival rate was 90.2% in the treatment group and 78.3% in the control group. Sample size was calculated using PASS.15 software, and Survival-Two Survival Curves-Test(Equality)-Logrank Tests were applied. set Power=0.8, α = 0.025 (unilateral), according to the control group and experimental group 1:1, combined with the basis of the previous research, taking the Proportion Surviving as Input Type, S1(Proportion Surviving - Control) = 0.783, S2(Proportion Surviving - Treatment) = 0.90, T0 (Survival Time) = 5 years, Accrual Time (Integers Only) = 2 years, uniform enrolment, the rate of shedding in each group is 10%, the calculation can be calculated to obtain a total sample size of 317 cases, 158 cases in the treatment group and 159 cases in the control group. At the same time, there are five clinical trial centres in this study, according to the sample size estimation requirements of multifactorial analysis, the introduction of one more confounding factor needs to increase the sample size of each group by 15-25 cases, and this study considers an increase of 20 cases in each group. Therefore, 178 cases need to be collected in each group, and the total sample size of the two groups is 356 cases (Table 2).

Table 2. Sample size estimation for each centre.

research centre	treatment group	control group	total
Shanghai Municipal Hospital of Traditional Chinese Medicine	38	38	76
Shanghai Pulmonary Hospital	35	35	70
Shanghai Chest Hospital	35	35	70
Shanghai General Hospital	35	35	70
Shanghai TCM-Integrated Hospital	35	35	70
total	178	178	356

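### At the protocol's own planning rates the median DFS and OS named in section 2.6.4 are expected to be not reached in either arm; a low-impact reporting flaw with a cheap repair

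*Protocol*

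**What the plan says.** Section 2.6.4 makes DFS the main efficacy indicator and says how it will be summarised: "Observation and follow-up until 5 years after surgery, disease-free survival rate, disease-free survival and median survival calculation". For OS it says: "Overall survival and median survival calculations were performed with observational follow-up up to 5 years postoperatively". Section 2.3 also ends observation at 5 years, or earlier at death or progression.

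The planning rates are in section 1.4. From the group's previous research, "the 5-year disease-free survival rate was 90.2% in the treatment group and 78.3% in the control group". The values entered in the sample size program are "S1(Proportion Surviving - Control) = 0.783" and "S2(Proportion Surviving - Treatment) = 0.90", with "T0 (Survival Time) = 5 years". No planning rate is given for OS.

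The Statistical Analysis section adds Kaplan-Meier curves for DFS and OS, a hazard ratio from a stratified Cox model, and 95% confidence intervals. The protocol does not say what is reported if a median is not reached.

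**The concern.** The median is the only summary on the time scale that the protocol names for DFS and OS. It can be read from a Kaplan-Meier curve only if that curve reaches 50% while patients are still observed. The trial is sized on the expectation that well over half of each arm is disease-free when observation stops, so sections 1.4 and 2.6.4 do not fit together.

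What is at stake is the description of benefit in units of time, which clinicians and patients will ask for. If both medians come out as not reached, a replacement would have to be chosen after the curves have been seen, unless one is named beforehand. The test, the hazard ratio and the sample size do not depend on the median.

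**Working it through.** **Inputs.** From section 1.4: S(5) = 0.783 (control) and 0.90 (treatment; 0.902 in the earlier research), a one-sided level ("α = 0.025 (unilateral"), power 0.80, equal allocation ("according to the control group and experimental group 1:1"), 10% loss, 317 patients before the centre allowance and 178 per arm after it. From section 2.6.4: observation to 5 years after surgery. From section 1.2: enrolment up to 6 weeks after surgery.

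**1. The plan's own figure.** HR = ln(0.90)/ln(0.783) = 0.431. Schoenfeld events = 4(1.960 + 0.842)²/(ln 0.431)² = 44.2, so 45. Mean 5-year event probability = (0.217 + 0.100)/2 = 0.1585. N = 45/0.1585 = 283.9, and 283.9/0.90 = 315.4, so 316 against 317 stated. This reading, with every patient observed for 5 years, reproduces the stated size. The two rates are therefore what the design rests on.

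**2. Is a median expected?** No distributional assumption is needed. At the end of observation the planned curves stand at 78.3% and 90%, both above 50%. OS cannot be shorter than DFS, so planned OS at 5 years is at least 78.3% and 90%.

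**3. How far away are the medians?** With exponential survival, h = −ln S(5)/5 and the median is ln 2/h.

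| Arm | S(5) | h per year | Median DFS, years |
|---|---|---|---|
| Control | 0.783 | 0.0489 | 14.2 |
| Treatment | 0.90 | 0.0211 | 32.9 |
| Treatment, earlier research | 0.902 | 0.0206 | 33.6 |

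To bring the median down to 5 years, the hazard would have to be 2.8 times (14.2/5) the planned control hazard or 6.6 times (32.9/5) the planned treatment hazard. If the planning rates are right and 178 per arm are fully observed, the binomial probability that at least half have an event by 5 years is about 1e-16 (control) and 2e-41 (treatment).

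**4. What if the planning rates are too optimistic?** The Background gives about 45.5% recurrence in stage II-III, with no time point, and 5-year survival of 49.3% in stage IIIA.
- If 45.5% is read as a 5-year control DFS event rate (an assumption), S(5) = 0.545 and the exponential median is 5.7 years. The standard error with 178 patients is √(0.545 × 0.455/178) = 0.037. The observed curve would end at or below 50% with probability Φ((0.50 − 0.545)/0.037), about 11%. Deaths without recurrence also count as DFS events and would raise this.
- At S(5) = 0.493 the exponential median is 4.9 years.
- With the planned HR, treatment S(5) would still be 0.545^0.431 = 0.77 or 0.493^0.431 = 0.74.

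So a control median may be reached under such rates. At the planned effect the treatment median is not, and a difference in medians is still unavailable.

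**5. Is there an estimable time-scale summary?** The restricted mean to time t is (1 − e^(−ht))/h. The standard error is the square root of the summed variances of min(T, t), each divided by 178, with no loss. Randomisation up to 6 weeks after surgery leaves at least 5 − 6/52 = 4.88 years from randomisation, so 4.5 years lies inside planned follow-up.

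| Horizon | Control, years | Treatment, years | Difference, months | SE, years | 95% half-width, months |
|---|---|---|---|---|---|
| 5 years | 4.44 | 4.75 | 3.7 | 0.116 | 2.7 |
| 4.5 years | 4.04 | 4.29 | 3.0 | 0.100 | 2.4 |

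If the planned 10% loss removed those patients entirely, which overstates it, about 160 per arm would remain and the 4.5-year half-width would be 2.35 × √(178/160) = 2.5 months.

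**The case against.** Little depends on the median. It is neither the test nor the effect measure, and the sample size does not use it. The sentence that plans it for DFS also lists a disease-free survival rate, and the Statistical Analysis section promises confidence intervals. A median reported as not reached is a legitimate Kaplan-Meier result and biases nothing. All of this stands, and it limits the weight of the point.

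A reader might infer that the medians cannot be estimated at all. The documents do not support that: it holds at the rates in section 1.4, but the Background describes worse outcomes, under which a control median might be reached. The very small probabilities in step 3 are conditional on the planning rates in the same way.

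A reader might also take 14 and 33 years as predictions for both endpoints. They are exponential extrapolations for DFS only. Without an OS planning rate they are no more than lower bounds for OS, and the argument does not need them.

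It could further be said that the summary to report when a median is missing belongs in the statistical analysis plan. Detail on that can go there. But this protocol itself names the median for the primary endpoint and for OS, and an analysis plan written to it would inherit the mismatch.

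Finally, restricted mean time for OS is no cure if deaths after recurrence go unrecorded. Section 2.3 allows observation to end at progression, and section 2.6.4 takes patients with confirmed recurrence out of the group. That objection stands and is dealt with in the fix.

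**Conclusion.** The point holds in limited form. At the protocol's own planning rates, 78.3% and 90% are disease-free when observation ends, so the medians named in section 2.6.4 are expected to be not reached in both arms, for DFS and for OS. This rests on those rates, on observation ending at 5 years, and on OS being at least as long as DFS. Only the 14- and 33-year figures need exponential survival.

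The impact is low. A tempting stronger reading is that the primary analysis is undermined, or that the hazard ratio would be left as an inadequate summary. The documents do not support it: the Kaplan-Meier and Cox analyses do not use the median, a DFS rate is already planned, and nothing in the protocol establishes that the hazard ratio would mislead. What is lost is a pre-specified summary on the time scale. A restricted mean difference could supply it, with a planned value of about 3 months to 4.5 years and a 95% half-width of about 2.4 months before loss.

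**What to change.** In section 2.6.4, for DFS and OS:
- report the median in an arm only if its curve reaches 50%;
- name as the time-scale summary the between-arm difference in restricted mean survival time to a fixed horizon inside planned follow-up, for example 4.5 years from randomisation, with a 95% confidence interval;
- give Kaplan-Meier DFS and OS rates at stated times, for example 3 years and the same 4.5-year horizon, with 95% confidence intervals;
- keep the stratified Cox hazard ratio as the primary effect measure.

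For OS, reconcile the end of observation at progression (section 2.3) and the removal of patients with recurrence (section 2.6.4) with the OS definition, which counts death from any cause. Deaths after recurrence need to be recorded for any OS summary to be valid.

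The cost is a few sentences and one more estimate from the same DFS data. OS needs no new data if deaths after recurrence are already collected; if they are not, follow-up for survival has to be added. Restricted mean time is less familiar to some readers, and its precision will be slightly worse than the 2.4-month half-width once the planned 10% loss is counted.
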